1.7 Research Hypotheses

- Primary Hypothesis: Avelumab treatment will result in an increase in CD3+CD4+ T-cell and CD3+CD8+ T-cell infiltrates.
- Secondary Hypotheses:
 - Pathological response rate will be comparable to historical controls receiving NA cisplatin based chemotherapy.
 - 2 year disease free survival (DFS) will be better than historical controls not receiving NAC and comparable to historical controls receiving cisplatin based NAC.
 - Avelumab will be safe and tolerable in our patient population.
 - Infiltration of regulatory B-cells will increase with avelumab treatment and increased levels will be associated with less response to treatment.
 - Increased COX-1 and COX-2 levels on transurethral resection of the bladder tumor (TURBT) tissue will be associated with decreased response to avelumab.

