3. STUDY DESIGN

3.1 Overview of Study Design

This is a pilot study of avelumab in patients with non-metastatic, MIBC who are eligible for RC, but refuse or are ineligible for cisplatin based NAC. The target recruitment is 10 evaluable patients for this window of opportunity study. Pre- and post-treatment tumor samples from TURBT and RC will be used for study endpoints.

Patients will be recruited from sites within the academic system of Baylor College of Medicine. Recruitment will be over one year and patients will undergo systemic treatment followed by surgery as per protocol. They will be followed for 2 years for survival, recurrence, and safety monitoring.

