3.4 Evaluability and Patient Replacement

Patients will continue to be enrolled on study until we have enrolled/treated 10 patients who are evaluable for the primary endpoint. Patients will be replaced after enrollment if they are later determined not to be evaluable for the primary endpoint.

Evaluable patients

- For primary endpoint
 - Receive \geq 1 dose of avelumab, undergo RC within 5 weeks of last dose of avelumab, and are not started on systemic steroids at a dose of > 10 mg/d of prednisone or equivalent, while taking avelumab.
- For safety endpoint
 - Receive \geq 1 dose of avelumab
- For pathologic complete response/partial response
 - Receive \geq 1 dose of avelumab and undergo RC < 42 days from last avelumab dose
- For 2 year disease free survival
 - Meet evaluability criteria for complete response/partial response, participate in 90 day on study follow-up after RC and participate in off study follow-up as part of regular care up to 2 years post RC.

Inevaluable patients

- Patients who receive < 1 dose of avelumab after study enrollment for any reason.

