7.2.5 Follow-up schedule

- Any patient receiving ≥ 1 dose of avelumab will be followed up to 90 days after RC (or end of last cycle of avelumab for those not receiving RC) to evaluate for safety. The indicated follow-up is outlined in the study calendar.
- Those patients evaluable for secondary endpoints will be followed up on study to day 90 after RC as outlined in the study calendar.
- After the safety monitoring period of 90 days post RC those patients who are evaluable for secondary endpoints will be followed off study for recurrence and survival for up to 2 years after RC. This may be done by physician visits/imaging performed approximately every 3 months for those undergoing surveillance at Baylor affiliates or by phone conversations approximately every 3 months for those undergoing surveillance at practices outside of Baylor affiliates.

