10.2 Statistical analysis

To see the change in T cells pre- and post-treatment, paired t-test or nonparametric Wilcoxon signed rank test will be used after checking its normality.

Pathological response rate will be estimated along with 95% confidence interval. Two year disease free survival will be calculated using Kaplan-Meier survival curves with estimates of median and 95% confidence interval. Patients who are decided not to be evaluable for the primary outcome will be considered evaluable for the safety analysis and secondary outcomes, such patients will be summarized descriptively. The correlation of translational studies with response parameters will be summarized descriptively. Changes from pre- and post- treatment will be assessed using paired tests. SAS software will be used for all statistical analyses.

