12.3 Study timetable and end of study

The end of the study will be defined as the time point 90 days after RC. The recruitment period is estimated to take place over a period of approximately 12 months.

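### Section 3.4 ties 2-year DFS evaluability to follow-up that begins only after day 90, so, read literally, a patient who dies within 90 days of a timely cystectomy is left out of the DFS set

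*Protocol*

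**What the plan says.** Protocol section 3.4 sets the DFS population by three conditions that must all hold. The first is to be evaluable for pathologic response: "Receive \geq 1 dose of avelumab and undergo RC < 42 days from last avelumab dose". The second and third are to "participate in 90 day on study follow-up after RC and participate in off study follow-up", the latter running up to 2 years post RC. No exception is made for death.

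Two sections fix when off-study follow-up starts. Section 7.2.5, third bullet: "After the safety monitoring period of 90 days post RC those patients who are evaluable for secondary endpoints will be followed off study". Section 12.3: "The end of the study will be defined as the time point 90 days after RC".

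Other text bears on the point less directly:

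- Section 7.2.5, second bullet, seems to put evaluability before follow-up: "Those patients evaluable for secondary endpoints will be followed up on study to day 90 after RC".
- Section 3.1 describes follow-up without an evaluability condition: "They will be followed for 2 years for survival, recurrence, and safety monitoring".
- Section 10.2 plans Kaplan-Meier for 2-year DFS and adds: "Patients who are decided not to be evaluable for the primary outcome will be considered evaluable for the safety analysis and secondary outcomes". The same sentence goes on to say that those patients are to be described in summary form only.
- Section 1.7 states the hypothesis that DFS serves: "2 year disease free survival (DFS) will be better than historical controls not receiving NAC". It also expects DFS comparable to historical controls who had cisplatin-based neoadjuvant chemotherapy.

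**The concern.** An analysis set for a time-to-event endpoint should be fixed by facts known at or before time zero. Here the third condition can be met only by someone still alive when off-study follow-up begins, about 90 days after RC. Membership of the set therefore depends on the outcome being measured.

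The patients lost in this way all died early, so the error has one direction: it raises 2-year DFS. The result is then set against historical controls, and nothing in the protocol says that those series were conditioned on surviving 90 days after surgery. An upward shift helps both parts of the 1.7 hypothesis.

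This is a rule that the protocol states, not a detail left for a statistical analysis plan. If a patient dies in the window, the team must either apply the rule and lose the event, or depart from it after seeing the outcome.

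**Working it through.** **Plan figures.** The protocol gives no DFS target, DFS power or 90-day mortality, so there is no DFS figure to reproduce. Its one power statement (section 10.1, about 80%) concerns the T-cell endpoint and does not bear on this point.

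**Step 1: trace patients through the rule.** Each has a timely RC.

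| Patient | Response criteria | On-study follow-up | Off-study follow-up (after day 90) | In the 3.4 DFS set? |
|---|---|---|---|---|
| Dies on day 60 | met | took part until death | cannot begin | no |
| Recurs on day 60, alive past day 90, stays in follow-up | met | met | met | yes |
| Dies in month 8, followed until then | met | met | took part until death | yes, if the 2 years are read as a ceiling |

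Only deaths before day 90 are lost.

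**Step 2: expected bias.** Let S be the true probability of being event-free at 2 years and p the probability of death by day 90, both among patients with a timely RC. Anyone event-free at 2 years was alive at day 90, so

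P(event-free at 2 years | alive at day 90) = S / (1 - p).

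With assumed values:

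| p (assumed) | 1/(1-p) | S = 50% | S = 60% | S = 70% |
|---|---|---|---|---|
| 2% | 1.020 | 51.0% | 61.2% | 71.4% |
| 5% | 1.053 | 52.6% | 63.2% | 73.7% |
| 10% | 1.111 | 55.6% | 66.7% | 77.8% |

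**Step 3: chance that it arises.** Take 10 patients, the target number evaluable for the primary endpoint (the DFS set could differ somewhat). The chance of at least one death by day 90 is 1 - (1 - p)^10, which is 18%, 40% and 65% for p = 2%, 5% and 10%.

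**Step 4: what one sample would show.** Assume 10 patients, one death by day 90, three later events and no censoring before 2 years.

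- All counted: 6/10 = 60.0%, exact 95% CI 26.2% to 87.8%.
- Early death removed: 6/9 = 66.7%, exact 95% CI 29.9% to 92.5%.
- Difference: 6.7 percentage points.

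With one early death and two to five later events, the difference runs from 7.8 down to 4.4 points. With two early deaths and two to five later events, it runs from 15.0 down to 7.5 points.

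**Step 5: drop-outs.** Repeat step 4 as a Kaplan-Meier calculation with events at months 6, 12 and 18, six patients event-free at month 24, and the tenth patient leaving at month 2. If the tenth patient died, the estimate is 60.0% with the death kept and 66.7% with it removed. If the tenth patient left event-free, it is 66.7% whether that patient is censored or removed. Drop-out before any event is therefore not part of the problem.

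**The case against.** The best defence is that nobody meant to exclude early deaths. Section 3.4 asks patients to take part in follow-up, not to complete it, and the 2 years read as a ceiling. Its own list of inevaluable patients names only those who received less than one dose. The second bullet of 7.2.5 speaks as if evaluability were already settled when follow-up starts. Kaplan-Meier is chosen because follow-up will be uneven. With about 10 patients any missing death would be visible, and the effect is small.

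Much of this stands as evidence of intent and as a limit on importance. None of it puts the early death back. Someone who dies on day 60 has taken no part in follow-up that starts after day 90, however leniently taking part is read. The inevaluable list is not exhaustive, since it also omits a late RC. Kaplan-Meier can use only the patients admitted to the set.

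A reader might infer more than the text supports in four places:

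- **That 3.1 and 7.2.5 define a rival DFS set.** They describe follow-up. The second bullet of 7.2.5 covers secondary endpoints in general, including safety and pathologic response, so it suggests that evaluability precedes follow-up without establishing it for DFS.
- **That 10.2 would count an early death in a patient who lost primary evaluability but not in one who kept it.** The rest of that sentence says such patients are summarized descriptively, so it does not clearly place them in the Kaplan-Meier estimate.
- **That all of the earliest events are lost.** Only deaths are. A recurrence before day 90 in a survivor stays in.
- **That 9.12 drops deaths within 90 days from survival analysis.** It is safety-reporting text and excludes nothing.

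**Conclusion.** The point holds in a narrow form. Taken literally, section 3.4 removes from the DFS set any patient who has a timely RC and dies before day 90, which makes 2-year DFS too high by a factor 1/(1-p). For a true value of 60% the overstatement is 1.2, 3.2 or 6.7 points at assumed 90-day mortality of 2%, 5% or 10%.

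This rests on three assumptions: the mortality range and event counts, which the protocol does not give; death counting as an event under the ordinary meaning of DFS; and section 3.4 being applied as written, which may not be the intent.

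The consequence is modest. DFS is secondary, no decision rule depends on it, and the shift is well within an interval such as 26% to 88%. It is still worth correcting, because the bias runs only upward, favours the stated hypothesis and is cheap to remove.

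**What to change.** In section 3.4, delete the two participation conditions, so that the DFS set is the existing response-evaluable set, which is known at RC. Add that deaths and recurrences within 90 days of RC count as DFS events. Align 7.2.5 so that follow-up is owed to that set and does not define it, and have 10.2 name the same set for the Kaplan-Meier estimate. General censoring rules can stay with the statistical analysis plan, and 9.12 needs no change.

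The cost is a wording amendment, with the sponsor and IRB review that 11.4 requires. No visits or data are added: section 7.2.5 already follows every treated patient to 90 days after RC, and 9.12 already requires deaths in that period to be reported or documented. The only other downside is a possibly slightly less favourable DFS estimate.

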4. SUBJECT SELECTION: PATIENT INITIALS: _____

4.1 Inclusion Criteria

- a) Have undergone TURBT showing newly diagnosed muscle invasive UCB (mixed histology is allowed if the predominant histology is UCC) within 6 weeks prior to cycle 1, day 1 of treatment.
- b) No prior systemic treatment for muscle invasive UCB
- c) Clinical T2-T4a disease
- d) No evidence of clinically positive lymph nodes or distant metastasis on computed tomography (CT) scans of chest and CT or magnetic resonance imaging (MRI) studies of the abdomen/pelvis. Imaging must be within 90 days of registration.
- e) Male or female subjects aged \geq 18 years old.
- f) Must have adequate kidney, liver, and bone marrow function within 30 days of registration, as follows:
 - a. Absolute neutrophil count (ANC) $\geq 1.5 \times 10^9/L$
 - b. platelet count $\geq 100 \times 10^9/L$
 - c. hemoglobin $\geq 9 \text{ g/dL}$ (may have been transfused)
 - d. Total bilirubin level $\leq 1.5 \times \text{ULN}$
 - e. AST and ALT levels $\leq 2.5 \times \text{ULN}$
 - f. Estimated creatinine clearance $\geq 30 \text{ mL/min}$ according to the Cockcroft-Gault formula
- g) Negative serum or urine pregnancy test at screening for women of childbearing potential (WOCBP), within 30 days of registration.
- h) Both male and female subjects must agree to use highly effective contraception (see Section 6.1 Table 8) while receiving avelumab and for at least 60 days after last avelumab treatment if the risk of conception exists.

Female patients must agree to inform study coordinator or investigator immediately if they think they have become pregnant during the study.
- i) Must have FFPE tissue available from the TURBT, and patient must consent to the use of tissue specimens from TURBT and RC for the study.
- j) Patients must have refused or have been determined to be ineligible for cisplatin-based NAC. Ineligibility criteria include: creatinine clearance $< 60 \text{ ml/min}$ by Cockcroft-Gault formula, CTCAE grade ≥ 2 hearing loss, CTCAE grade ≥ 2 neuropathy, and at discretion of medical oncologist.

If a patient is eligible for cisplatin-based NAC but has refused it, the reason for refusal must be documented in the patient record.
- k) Must be eligible for RC in the opinion of the treating investigator, and willing to undergo this procedure.
- l) ECOG performance status (PS) score of 0-2
- m) Signed informed consent form.

4.2 Exclusion Criteria

Patients must not have any of the following:

- a) IMMUNOSUPPRESSANTS: Current use of immunosuppressive medication or within 4 weeks of C1D1, EXCEPT for the following: a. intranasal, inhaled, topical steroids, or local steroid injection (e.g., intra-articular injection); b. Systemic corticosteroids at physiologic doses \leq 10 mg/day of prednisone or equivalent; c. Steroids as premedication for hypersensitivity reactions (e.g., CT scan premedication).
- b) AUTOIMMUNE DISEASE: Active autoimmune disease that might deteriorate when receiving an immuno-stimulatory agent. Patients with diabetes type I, vitiligo, psoriasis, or hypo- or hyperthyroid diseases not requiring immunosuppressive treatment are eligible. Patients with type I diabetes or hypo- or hyperthyroidism should be on stable doses of medications for participation.
- c) ORGAN TRANSPLANTATION: Prior organ transplantation including allogenic stem-cell transplantation.
- d) INFECTIONS: Active infection requiring systemic therapy.
- e) HIV/AIDS: Known history of testing positive for HIV or known acquired immunodeficiency syndrome.
- f) HEPATITIS: Hepatitis B virus (HBV) or hepatitis C virus (HCV) infection at screening (positive HBV surface antigen or HCV RNA if anti-HCV antibody screening test positive)
- g) VACCINATION: Vaccinate within 4 weeks of the first dose of avelumab and while on study drug is prohibited except for administration of inactivated vaccines
- h) HYPERSENSITIVITY TO STUDY DRUG: Known prior severe hypersensitivity to investigational product or any component in its formulations, including known severe hypersensitivity reactions to monoclonal antibodies (NCI CTCAE v4.03 Grade \geq 3)
- i) CARDIOVASCULAR DISEASE: Clinically significant (i.e., active) cardiovascular disease: cerebral vascular accident/stroke ($<$ 6 months prior to enrollment), myocardial infarction ($<$ 6 months prior to enrollment), unstable angina, congestive heart failure (\geq New York Heart Association Classification Class II), or serious cardiac arrhythmia requiring medication.
- j) Other severe acute or chronic medical conditions including colitis, inflammatory bowel disease, pneumonitis, pulmonary fibrosis or psychiatric conditions including recent (within the past year) or active suicidal ideation or behavior; or laboratory abnormalities that may increase the risk associated with study participation or study treatment administration or may interfere with the interpretation of study results and, in the judgment of the investigator, would make the patient inappropriate for entry into this study.
- k) Relapsed MIBC (all patients participating in the study should be newly diagnosed)
- l) Concomitant UCC outside the bladder (e.g., ureter, urethra or renal pelvis)
- m) Underlying immune disorder (e.g., combined variable immunodeficiency syndrome)

- n) Erythropoietin receptor agonists within 30 days prior to enrollment.
- o) G-CSF, GM-CSF or TPO mimetics during the study period or within 3 weeks prior to study enrollment
- p) Malignancies other than UCB within 5 years prior to Cycle 1, Day 1, with the exception of those with low risk of metastasis or death treated with expected curative outcome (such as, but not limited to, adequately treated carcinoma in situ of the cervix, basal or squamous cell skin cancer, localized prostate cancer treated with curative intent and absence of PSA relapse, or ductal carcinoma in situ of the breast treated surgically with curative intent) or incidental prostate cancer (T1a, Gleason score ≤ 6 and PSA < 0.5 ng/ml)
- q) Prior immunotherapy with T-cell co-stimulation or checkpoint targeted agents (e.g., CTLA-4 inhibitors, anti-PD1 antibodies or anti-PD-L1 antibodies)
- r) Intravesical chemotherapy or biologic therapy within 6 weeks of Cycle 1, Day 1
- s) Current participation in another clinical trial for MIBC
- t) Nursing or pregnant woman
- u) Uncontrolled cystitis, significant bladder pain or spasms, or gross hematuria that in the opinion of the principal investigator will preclude study participation
- v) Major surgical procedures within 4 weeks of registration (other than for diagnosis) or anticipation that such a procedure will be needed during the study (other than RC)

Treating Investigator Name: _____

Treating Investigator Signature: _____

Date: _____

4.3 Withdrawal of Subjects from Study Treatment and/or Study

An individual subject will not receive any further investigational product if any of the following occur after enrollment on study:

- Withdrawal of consent by subject
- Subject is determined to have met one or more of the exclusion criteria for study participation at study entry and continuing investigational therapy might constitute a safety risk
- Pregnancy or intent to become pregnant
- Any criteria that necessitates discontinuation of study treatment as outlined in sections 5.5-5.7
- Subject noncompliance that in the opinion of the investigator or sponsor warrants withdrawal; e.g., refusal to adhere to scheduled visits
- Initiation of alternative anticancer therapy including another investigational agent
- Subject has > 2 week delay in the administration of avelumab. Such patients will still receive surgery and laboratory/clinical follow-up to complete the 90 day safety monitoring after RC. Some of these patients may be evaluable for primary and/or secondary outcomes.

Subjects who are permanently discontinued from further receipt of avelumab, regardless of the reason, will be identified as having permanently discontinued treatment.

- **Withdrawal of consent**

Patients are free to withdraw their consent to further participation in this trial without prejudice. If consent is withdrawn, the subject will not receive any further investigational product.

- **Withdrawal from study**

Patients determined to be inevaluable will be removed from study. Such patients will receive standard of care and follow-up. Such patients will be followed off study for recurrence and/or survival as part of routine care.

5. TREATMENT PLAN

5.1 Premedication

The following will be administered 30-60 minutes prior to avelumab

- Diphenhydramine: 25 mg IV, or 25-50 mg PO
- Paracetamol (acetaminophen): 500 to 650 mg PO

5.2 Dosage and Administration of Avelumab

- Avelumab will be given at a dose of 10 mg/kg IV over 60 minutes every 2 weeks (Days 1, 15, and 29), for 3 cycles. Each cycle is 14 days.
- Drug will be given in outpatient infusion centers, all of which have immediate access to emergency services or critical care. The following medications or equivalents will be immediately available in the case of a severe allergic reaction: 10 mg dexamethasone, epinephrine (1:1000 dilution), IV anti-histamines, bronchodilators and oxygen.
- Patients will be observed for 2 hours post-infusion to monitor for infusion reactions.

5.3 Radical Cystectomy (RC)

- Patients will undergo RC within five weeks after the 3rd dose of avelumab.
- Cystectomy will be done per standard clinical care.

5.4 Supportive Care

- Patients will receive supportive care for acute or chronic toxicity, including blood components or antibiotics, and other intervention as appropriate

5.5 Table 5: Adverse Drug Reactions Requiring Avelumab Discontinuation or Modification

Any Grade 4 ADR requires treatment discontinuation with avelumab, except for single laboratory values out of normal range that are unlikely related to study treatment as assessed by the Investigator, do not have any clinical correlate, and resolve within 7 days with adequate medical management.

Any Grade 3 ADR requires treatment discontinuation with avelumab except for any of the following:

- Transient (\leq 6 hours) Grade 3 flu-like symptoms or fever, which is controlled with medical management
- Transient (\leq 24 hours) Grade 3 fatigue, local reactions, headache, nausea, emesis that resolves to Grade \leq 1
- Single laboratory values out of normal range (excluding Grade \geq 3 liver function test increase) that are unlikely related to study treatment according to the Investigator, do not have any clinical correlate, and resolve to Grade \leq 1 within 7 days with adequate medical management
- Tumor flare phenomenon defined as local pain, irritation, or rash localized at sites of known or suspected tumor

- Change in ECOG PS to ≥ 3 that resolves to ≤ 2 within 14 days (infusions should not be given on the following cycle, if the ECOG PS is ≥ 3 on the day of study drug administration)

Any Grade 2 ADR should be managed as follows:

- If a Grade 2 ADR resolves to Grade ≤ 1 by the last day of the current cycle, treatment may continue.
- If a Grade 2 ADR does not resolve to Grade ≤ 1 by the last day of the current cycle, infusions should not be given on the following cycle. If at the end of the following cycle the event has not resolved to Grade 1, the subject should permanently discontinue treatment with avelumab ADR (except for hormone insufficiencies that can be managed by replacement therapy).
- Upon the second occurrence of the same Grade 2 ADR (except for hormone insufficiencies that can be managed by replacement therapy) in the same subject, treatment with avelumab has to be permanently discontinued.

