5.7 Table 7: Management of Immune-Related Adverse Reactions

Since inhibition of PD-L1 stimulates the immune system, immune-related AEs (irAEs) may occur. Treatment of irAEs is mainly dependent upon severity (NCI-CTCAE grade):

- Grade 1 to 2: treat symptomatically or with moderate dose steroids, more frequent monitoring
- Grade 1 to 2 (persistent): manage similar to high grade AE (Grade 3 to 4)
- Grade 3 to 4: treat with high dose corticosteroids

Treatment of gastrointestinal, dermatological, pulmonary, hepatic, endocrine and cardiac irAEs should follow guidelines set forth in the table below.

Gastrointestinal irAEs		
Severity of Diarrhea / Colitis (NCI-CTCAE v4.03)	Management	Follow-up
Grade 1 Diarrhea: < 4 stools/day over baseline Colitis: asymptomatic	Continue avelumab therapy Symptomatic treatment (for example, loperamide)	Close monitoring for worsening symptoms Educate subject to report worsening immediately If worsens: Treat as Grade 2 or 3/4
Grade 2 Diarrhea: 4 to 6 stools per day over baseline; IV fluids indicated < 24 hours; not interfering with ADL Colitis: abdominal pain; blood in stool	Delay avelumab therapy unless systemic steroids needed. If systemic steroids are needed, discontinue avelumab. Symptomatic treatment	If improves to Grade 1: Resume avelumab therapy If persists > 5 to 7 days or recurs: 0.5 to 1.0 mg/kg/day methylprednisolone or equivalent; when symptoms improve to Grade 1, taper steroids over at least 1 month, consider prophylactic antibiotics for opportunistic infections and remove patient from study treatment. If worsens or persists > 3 to 5 days with oral steroids: Treat as Grade 3 to 4
Grade 3 to 4 Diarrhea (Grade 3): ≥ 7 stools per day over baseline; incontinence; IV fluids ≥ 24 hrs.; interfering with ADL	Discontinue avelumab therapy per protocol 1.0 to 2.0 mg/kg/day methylprednisolone IV or equivalent	If improves: Continue steroids until Grade 1, then taper over at least 1 month If persists > 3 to 5 days, or recurs after improvement:

Colitis (Grade 3): severe abdominal pain, medical intervention indicated, peritoneal signs Grade 4: life-threatening, perforation	Add prophylactic antibiotics for opportunistic infections Consider lower endoscopy	Add infliximab 5 mg/kg (if no contraindication), Note: Infliximab should not be used in cases of perforation or sepsis
--	---	--

Dermatological irAEs

Grade of Rash (NCI-CTCAE v4)	Management	Follow-up

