Grade 1 AST or ALT > ULN to 3.0 x ULN and / or total bilirubin > ULN to 1.5 x ULN	Continue avelumab therapy	Continue liver function monitoring If worsens: Treat as Grade 2 or 3 to 4
Grade 2 AST or ALT > 3.0 to \leq 5 x ULN and / or total bilirubin > 1.5 to \leq 3 x ULN	Delay avelumab therapy. If systemic steroids are required, avelumab therapy will be discontinued. Increase frequency of monitoring to every 3 days	If returns to Baseline: Resume routine monitoring, resume avelumab therapy If elevations persist > 5 to 7 days or worsens: 0.5 to 1 mg/kg/day methylprednisolone or oral equivalent and when LFT returns to grade 1 or baseline, taper steroids over at least 1 month, consider prophylactic antibiotics for opportunistic infections, and discontinue avelumab therapy

Grade 3 to 4 AST or ALT > 5 x ULN and / or total bilirubin > 3 x ULN
	
Discontinue avelumab therapy Increase frequency of monitoring to every 1 to 2 days 1.0 to 2.0 mg/kg/day methylprednisolone IV or IV equivalent Add prophylactic antibiotics for opportunistic infections Consult gastroenterologist Consider obtaining MRI/CT scan of liver and liver biopsy if clinically warranted
	
If returns to Grade 2: Taper steroids over at least 1 month If does not improve in > 3 to 5 days, worsens or rebounds: Add mycophenolate mofetil 1 gram (g) twice daily If no response within an additional 3 to 5 days, consider other immunosuppressants per local guidelines

Endocrine irAEs		
Endocrine Disorder	Management	Follow-up
Asymptomatic TSH abnormality	
Continue avelumab therapy If TSH < 0.5 x LLN, or TSH > 2 x ULN, or consistently out of range in 2 subsequent measurements: include T4 at subsequent cycles as clinically indicated; consider endocrinology consult
	
Symptomatic endocrinopathy	
Evaluate endocrine function Consider pituitary scan Symptomatic with abnormal lab / pituitary scan: Discontinue avelumab therapy 1 to 2 mg/kg/day methylprednisolone IV or by mouth equivalent (with the exception of diabetes mellitus)
	
If improves (with or without hormone replacement): Taper steroids over at least 1 month and consider prophylactic antibiotics for opportunistic infections Subjects with adrenal insufficiency may need to continue steroids with mineralocorticoid component

	
Initiate appropriate hormone therapy
 
No abnormal lab / pituitary MRI scan but symptoms persist: Repeat labs in 1 to 3 weeks / MRI in 1 month
	

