3. Laboratory analysis on day 15 and day 29 may be performed on the day of infusion if results are received prior to avelumab administration. Alternatively, these laboratory analysis may be performed the day prior to avelumab administration.
4. The **end of treatment visit** (post-treatment pre-surgery) should be performed between days 40 and 50.
5. The **end of study visit** should be 90 days after surgery +/- 10 days.
6. On-treatment visits with history and physical exam should be ≤ 3 days before a scheduled dose of avelumab.
7. RC may be done any time after the pre-surgery evaluation is completed, but no later than day 64.
8. History and physical exams performed after RC (with the exception of the end of study visit) have a time window of +/- 7 days.
9. Post-operative labs up to day 60 after RC have a time window of +/- 7 days.

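### As written, Table 5 stops avelumab for an isolated Grade 3 liver-test rise but not for the same rise at Grade 4

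*Protocol*

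**What the plan says.** Table 5 in protocol section 5.5 sets individual stopping rules by grade.

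- **Grade 4:** any adverse drug reaction ends avelumab, "except for single laboratory values out of normal range that are unlikely related to study treatment as assessed by the Investigator". The value must also have no clinical correlate and resolve within 7 days with medical management. Liver tests are not mentioned.
- **Grade 3:** any adverse drug reaction ends avelumab unless a listed exception applies. One exception covers single laboratory values, but its bracket removes liver-test rises of Grade 3 or higher. From inside the bracket the bullet runs "liver function test increase) that are unlikely related to study treatment according to the Investigator". The value must come down to Grade 1 or lower within 7 days.

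Three other sections bear on the point.

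- **Section 4.3** stops drug for "Any criteria that necessitates discontinuation of study treatment as outlined in sections 5.5-5.7", and separately where there is more than a "2 week delay in the administration of avelumab".
- **Section 5.7** introduces Table 7 with "Treatment of gastrointestinal, dermatological, pulmonary, hepatic, endocrine and cardiac irAEs should follow guidelines set forth in the table below". Its hepatic row for Grades 3 to 4 (AST or ALT above 5 x ULN and/or total bilirubin above 3 x ULN) says "Discontinue avelumab therapy Increase frequency of monitoring to every 1 to 2 days".
- **Sections 5.2 and 7.1** fix the timing. Avelumab is given "every 2 weeks (Days 1, 15, and 29), for 3 cycles". The day 15 and day 29 laboratory tests "may be performed on the day of infusion if results are received prior to avelumab administration", or they may be done the day before.

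**The concern.** A stopping rule for toxicity should not become more lenient as the event becomes more severe. Within Table 5 it does so for liver tests: the Grade 3 exception closes the door on them and the Grade 4 exception leaves it open. The Grade 4 exception is a separate sentence placed before the Grade 3 list, and nothing carries the Grade 3 bracket back to it.

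What is at stake is the safety of an individual patient. Someone with a Grade 4 liver-test rise could be redosed on the strength of one investigator's attribution, in a protocol that otherwise treats the liver with care. Hepatotoxicity is an adverse event of special interest (section 9.3), Hy's Law cases are reported as serious (section 9.11), and Table 7 delays dosing even for a Grade 2 elevation. Sample size, power and the primary analysis are not involved.

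**Working it through.** The plan gives no figure to reproduce. The check is a comparison of rules followed by a short calendar calculation.

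**Step 1. One event under both Table 5 rules.** Take an isolated liver-test rise that is judged unlikely to be related, has no clinical correlate, and falls to Grade 1 or lower within 7 days.

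| Condition | Grade 3 rule | Grade 4 rule |
|---|---|---|
| Single laboratory value | met | met |
| Judged unlikely related | met | met |
| No clinical correlate | met | met |
| Resolution within 7 days | met (to Grade 1 or lower) | met (no grade named) |
| Liver tests excluded from the exception? | yes | no |
| Table 5 result | discontinue | discontinuation not required |

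The only row that changes the result is the liver-test exclusion.

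**Step 2. Does Table 7 close the gap?** Where the hepatic row applies, it does. It discontinues at Grades 3 and 4, and under section 4.3 any single criterion in sections 5.5 to 5.7 is enough. However, section 5.7 presents Table 7 as management of immune-related events. The Table 5 exception concerns precisely those rises judged unlikely to be due to treatment, which a site may not classify as immune-related. For that group Table 7 does not clearly apply.

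**Step 3. Does the delay rule close the gap?** Inputs: doses on days 1, 15 and 29 (section 5.2); resolution within 7 days (section 5.5); drug stopped only after a delay of more than 14 days (section 4.3); results in hand before the day 15 and day 29 doses (section 7.1).

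- Found at the day 15 test: latest resolution is day 15 + 7 = day 22. The delay limit is day 15 + 14 = day 29. Since 22 < 29, doses 2 and 3 remain possible: up to 2 of 3.
- Found at the day 29 test: latest resolution is day 29 + 7 = day 36. The delay limit is day 29 + 14 = day 43. Since 36 < 43, dose 3 remains possible: 1 of 3.
- Found after dose 3: 0 of 3.

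An unresolved Grade 4 value does not qualify for the exception on the day it is found. The exposure at issue is redosing after resolution, and the delay rule does not prevent it.

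**Step 4. Frequency.** The protocol gives neither a Grade 4 liver-test rate for avelumab nor a split by attribution, so the probability cannot be derived.

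**The case against.** The strongest reply is that the rest of the protocol already covers this. The Table 7 hepatic row is triggered by numerical thresholds, contains no attribution test of its own, and reaches the patient through section 4.3. Section 9.5 also lists transaminase and bilirubin elevations among the signs of immune-mediated hepatitis. This stands in part: a Grade 4 rise handled as an immune-related event does end avelumab. It does not settle the case of a rise judged unlikely to be related, because the scope of Table 7 comes from its introduction and headings. And if Table 7 stopped drug for every Grade 3 to 4 rise regardless of cause, the liver exclusion in the Grade 3 exception would be redundant.

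A second reply is that the at-or-above sign in the Grade 3 bracket shows Grade 4 was meant to be included. That is probably right, and it makes this a drafting omission. It also means the intended rule is absent from the sentence that governs Grade 4.

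A third is that the reasoning applies attribution unevenly. Table 5 governs adverse drug reactions, so a rise unlikely to be related might fall outside Table 5 as well. But the Table 5 exceptions deal expressly with values judged unlikely to be related, so Table 5 treats them as within its scope. Table 7 has no equivalent.

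Other limits stand. The exception lifts mandatory discontinuation and does not oblige anyone to redose. With 10 evaluable patients in one academic system under close oversight by the principal investigator, divergent readings between sites are a weak concern. The missing target grade in the Grade 4 sentence is minor, since resolution there may mean full resolution.

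**Conclusion.** The point holds. On its wording, Table 5 is not monotone in severity for liver tests: the Grade 3 rise ends avelumab and the otherwise identical Grade 4 rise need not. At most 2 of 3 doses are exposed if the value is found on day 15, 1 of 3 if on day 29, and none after dose 3. These are worst cases conditional on the event and do not describe an expected impact.

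The conclusion assumes that the rise meets every condition of the exception and is not managed under Table 7 as immune-related. Any other Grade 4 liver-test rise still ends treatment. The event should be rare, and the primary endpoint is essentially unaffected. The change should be made because an operative safety rule should state its meaning directly.

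**What to change.** In the Grade 4 sentence of Table 5, add *(excluding liver function test increase)* after the reference to single laboratory values. For clarity, also require resolution to Grade 1 or lower within 7 days, matching the Grade 3 bullet.

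Alternatively, state in section 5.7 that the hepatic row of Table 7 governs all Grade 3 to 4 liver-test elevations, whatever their attributed cause.

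Either is a one-sentence protocol amendment and adds no patients, visits or procedures.
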